5.2.4 Labeling, Packaging, Storage and Return Of Clinical Supplies

5.2.4.1 Investigational Product

The investigator shall take responsibility for and shall take all steps to maintain appropriate records and ensure appropriate supply, storage, handling, distribution and usage of investigational products in accordance with the protocol and any applicable laws and regulations.

Pembrolizumab and Lenvatinib will be provided by Merck as summarized in Table 8.

Table 8 Product Descriptions

Product Name & Potency	Dosage Form
Pembrolizumab 100 mg/ 4mL	Solution for Injection
Lenvatinib 10 and 4 mg capsules	Oral

5.2.4.2 Packaging and Labeling Information

Supplies will be labeled in accordance with regulatory requirements.

5.2.4.3 Clinical Supplies Disclosure

This trial is open-label; therefore, the participant, the trial site personnel, the Sponsor and/or designee are not blinded to treatment. Drug identity (name, strength) is included in the label text; random code/disclosure envelopes or lists are not provided.

5.2.4.4 Storage and Handling Requirements

Confidential

Clinical supplies must be stored in a secure, limited-access location under the storage conditions specified on the label.

Receipt and dispensing of trial medication must be recorded by an authorized person at the trial site.

Clinical supplies may not be used for any purpose other than that stated in the protocol.

5.2.4.5 Returns and Reconciliation

The investigator is responsible for keeping accurate records of the clinical supplies received from Merck or designee, the amount dispensed to and returned by the participants and the amount remaining at the conclusion of the trial.

Upon completion or termination of the study, all unused and/or partially used investigational product will be destroyed at the site per institutional policy. It is the Investigator's responsibility to arrange for disposal of all empty containers, provided that procedures for proper disposal have been established according to applicable federal, state, local and institutional guidelines and procedures, and provided that appropriate records of disposal are kept.

5.3 Concomitant Medications/Vaccinations (allowed & prohibited)

The investigator or qualified designee will record medication, if any, taken by the participant during the study. Concomitant medications will be recorded for 30 days after the last dose of study intervention. Medications or vaccinations specifically prohibited in the exclusion criteria are not allowed during the ongoing trial. If there is a clinical indication for one of these or other medications or vaccinations specifically prohibited from trial therapy or vaccination may be required. The final decision on any supportive therapy or vaccination rests with the investigator and/or the participant's primary physician. However, the decision to continue the participant on study intervention requires the mutual agreement of the investigator, the Sponsor, and the participant.

5.3.1 Acceptable Concomitant Medications

All treatments that the investigator considers necessary for a participant's welfare may be administered at the discretion of the investigator in keeping with the community standards of medical care. All concomitant medication will be recorded on the case report form (CRF) including all prescription, over-the-counter (OTC), herbal supplements, and IV medications and fluids. If changes occur during the trial period, documentation of drug dosage, frequency, route, and date may also be included on the CRF.

All concomitant medications received within 28 days prior to the first dose of trial intervention and up to 30 days after the last dose of trial intervention should be recorded. If participants experience an SAE or ECI, concomitant medications administered30 days after the last dose of trial intervention are to be recorded as defined in Section 6.2.

5.3.2 Prohibited Concomitant Medications

Participants are prohibited from receiving the following therapies during the Screening and Treatment Phase (including retreatment for post-complete response relapse) of this trial:

- Antineoplastic systemic chemotherapy or biological therapy
- Immunotherapy not specified in this protocol
- Chemotherapy not specified in this protocol
- Investigational agents other than pembrolizumab
- Radiation therapy
- Live vaccines within 30 days prior to the first dose of study treatment and while participating in the study. Examples of live vaccines include, but are not limited to, the following: measles, mumps, rubella, varicella/zoster, yellow fever, rabies, BCG, and typhoid vaccine. Seasonal influenza and mRNA vaccines for injection are generally killed virus vaccines and are allowed; however, intranasal influenza vaccines (e.g., FluMist®) are live attenuated vaccines and are not allowed.
- Systemic glucocorticoids for any purpose other than to modulate symptoms from an event of clinical interest of suspected immunologic etiology. The use of physiologic doses of corticosteroids may be approved after consultation with the Sponsor.

Participants who, in the assessment by the investigator, require the use of any of the aforementioned treatments for clinical management should be removed from the study. All treatments that the Investigator considers necessary for a participant's welfare may be administered at the discretion of the Investigator in keeping with the community standards of medical care.

Medications or vaccinations specifically prohibited in the exclusion criteria are not allowed during the ongoing study. If there is a clinical indication for any medication or vaccination specifically prohibited during the study, discontinuation from study therapy or vaccination may be required. The final decision on any supportive therapy or vaccination rests with the investigator and/or the participant's primary physician. There are no prohibited therapies during the Post-Treatment Follow-up Phase.

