5.4 Participant Discontinuation Criteria

Discontinuation of study intervention does not represent withdrawal from the study.

As certain data on clinical events beyond study intervention discontinuation may be important to the study, they must be collected through the participant's last scheduled follow-up, even if the participant has discontinued study intervention. Therefore, all participants who discontinue study intervention prior to completion of the protocol-specified treatment period will still continue to be monitored in this study and participate in the study visits and procedures as specified in Section 2.3 unless the participant has withdrawn from the study (Section 5.5).

Participants may discontinue study intervention at any time for any reason or be discontinued from the study intervention at the discretion of the investigator should any untoward effect occur. In addition, a participant may be discontinued from study intervention by the investigator or the Sponsor if study intervention is inappropriate, the study plan is violated, or for administrative and/or other safety reasons.

A participant must be discontinued from study treatment but continue to be monitored in the study for any of the following reasons:

- The participant or participant's legally acceptable representative requests to discontinue study intervention
- After prolonged study intervention interruption that prohibits restarting study intervention if agreed upon with the Sponsor
- Radiographic disease progression outlined in Section 6.1.4.
- Any progression or recurrence of any malignancy, or any occurrence of another malignancy that requires active treatment
- Any study intervention-related toxicity specified as a reason for permanent discontinuation as defined in the guidelines for dose modification due to AEs in Section 5.2.2.
- The participant has a medical condition or personal circumstance which, in the opinion of the investigator and/or sponsor, placed the participant at unnecessary risk from continued administration of study treatment.
- The participant has a confirmed positive serum pregnancy test

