5.5 Participant withdrawal From Study

A participant must be withdrawn from the study if the participant or the participant's legally acceptable representative withdraws consent from the study.

If a participant withdraws from the study, they will no longer receive study intervention or be followed at scheduled protocol visits.

Specified details regarding procedures to be performed at the time of withdrawal from the study are outlined in Section 6.1.6.1.

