6.1.4.4 RECIST 1.1 Assessment of Disease

RECIST 1.1 will be used as the primary measure for assessment of tumor response, date of disease progression, and as a basis for all protocol guidelines related to disease status (eg, discontinuation of study treatment). Although RECIST 1.1 references a maximum of 5 target lesions in total and 2 per organ, the Sponsor allows a maximum of 10 target lesions in total and 5 per organ, if clinically relevant to enable a broader sampling of tumor burden. The first half of the flowchart in [Figure 2] illustrates the imaging flow involving verification of PD for clinically stable participants.

6.1.4.5 iRECIST Assessment of Disease

iRECIST is based on RECIST 1.1, but adapted to account for the unique tumor response seen with immunotherapeutic drugs. iRECIST will be used by the investigator to assess tumor response and progression and make treatment decisions. When clinically stable, participants should not be discontinued until progression is confirmed by the investigator, working with local radiology, according to the rules outlined in Appendix 4. This allowance to continue treatment despite initial radiologic disease progression takes into account the observation that some participants can have

a transient tumor flare in the first few months after the start of immunotherapy, and then experience subsequent disease response. This data will be captured in the clinical database.

Clinical stability is defined as the following:

- Absence of symptoms and signs indicating clinically significant progression of disease
- No decline in ECOG performance status
- No requirements for intensified management, including increased analgesia, radiation, or other palliative care

Any participant deemed clinically unstable should be discontinued from study intervention at central verification of site-assessed first radiologic evidence of disease progression, and is not required to have repeat tumor imaging for confirmation of disease progression by iRECIST.

If the investigator decides to continue treatment, the participant may continue to receive study intervention and the tumor assessment should be repeated 4 to 8 weeks later to confirm disease progression by iRECIST, per investigator assessment. Images should continue to be sent in to the iCRO for potential retrospective BICR.

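### Section 5.3.2 tells sites to remove from the study participants who need a prohibited treatment, in conflict with Sections 5.4, 5.5, 6.1.1.6.3 and 6.1.7.3.3; applied literally, this loses PFS and OS follow-up

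*Combined protocol and SAP*

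**What the plan says.** Section 5.3.2 prohibits, during screening and treatment, other systemic anticancer therapy and immunotherapy, other investigational agents, radiation, live vaccines and most systemic glucocorticoids. It then says that participants who "require the use of any of the aforementioned treatments for clinical management should be removed from the study". The next paragraph of the same section gives a milder consequence: where something prohibited is clinically indicated, "discontinuation from study therapy or vaccination may be required". The section closes by lifting all prohibitions in post-treatment follow-up.

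Section 5.4 states: "Discontinuation of study intervention does not represent withdrawal from the study". Those who stop early "will still continue to be monitored in this study and participate in the study visits and procedures as specified in Section 2.3", except participants withdrawn under Section 5.5. The only ground in Section 5.5 is consent: "A participant must be withdrawn from the study if the participant or the participant's legally acceptable representative withdraws consent from the study". After withdrawal, "they will no longer receive study intervention or be followed at scheduled protocol visits".

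Two further sections bear on this. Section 6.1.1.6.3 moves anyone who starts a new anticancer therapy into survival follow-up. Section 6.1.7.3.3 ends survival contacts only at death, withdrawal of consent or end of study.

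**The concern.** The removal sentence creates a way out of the study that Section 5.5 does not list and Section 5.4 rules out. A site that follows it would stop scans and survival contacts for a participant who has not withdrawn consent.

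PFS is the primary endpoint and OS is secondary. Removal close to an undocumented progression would censor that participant for a reason related to the outcome, and this tends to lengthen apparent PFS. The protocol itself supports such a link for one class. Its definition of clinical stability in Section 6.1.4.5 includes "No requirements for intensified management, including increased analgesia, radiation, or other palliative care", so a need for radiation counts against stability.

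Section 7 gives no censoring rule for PFS or OS, so nothing in the analysis plan would limit the effect. The trial has a single arm, is read against historical medians, and has a 6-month median PFS threshold in its interim rule. No control arm would share the bias.

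**Working it through.** **Plan's own figures.** The plan gives no figure for loss from follow-up. Its only computed figures are the ORR powers in Section 7.2 (0.55, 0.78 and 0.91). A one-sided normal approximation with 30 participants reproduces them (0.554, 0.776 and 0.906), and they are not in dispute here.

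**Step 1: what the removal sentence adds, by class.** The comparison is with follow-up under the rest of the protocol.

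| Prohibited class | Follow-up without the removal sentence | What literal removal adds | Link to progression in the documents |
|---|---|---|---|
| Other anticancer treatment | Imaging stops when it starts (6.1.4.3, 6.1.7.3.2); survival contacts continue (6.1.1.6.3, 6.1.7.3.3) | Little for PFS; survival contacts lost | None stated in 5.3.2 |
| Radiation | Not stated whether it counts as new anticancer treatment; if not, imaging continues | Remaining scans lost (if it does not count) and survival contacts lost | Counts against clinical stability (6.1.4.5) |
| Systemic glucocorticoids outside the exceptions | Imaging and survival contacts continue | Both lost | None stated |
| Live vaccines | Imaging and survival contacts continue | Both lost | None stated |

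**Step 2: which PFS events are at risk.** Progression already documented is a PFS event and cannot be lost. Section 6.1.4.3 calls for a scan at treatment discontinuation (within 4 weeks either side, unless one was done in the preceding 4 weeks). Section 6.1.4 counts unscheduled imaging that shows progression. Only progression or death that these routes miss is at risk.

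**Step 3: illustration of size.** Inputs are the historical median PFS of 3.5 months and the 6-month interim threshold (Section 7.2), and the ipilimumab + nivolumab median of 5.5 months (Section 4.1). Assume exponential PFS with median m, and that a share p of events is censored at the moment the event would have occurred. The observed event hazard is then (1 − p) × ln 2 / m, and the Kaplan–Meier median tends to m / (1 − p). The documents give no value for p, so 10% to 30% is an assumed range.

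- m = 3.5: 3.5/0.9 = 3.9; 3.5/0.8 = 4.4; 3.5/0.7 = 5.0 months.
- Share needed for 3.5 months to read as 6: 1 − 3.5/6 = 42%.
- m = 5.5: 5.5/0.9 = 6.1; 5.5/0.8 = 6.9; 5.5/0.7 = 7.9 months. Share needed to read as 6: 1 − 5.5/6 = 8%.

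A simulation under the same assumptions (15 participants, true median 3.5 months, 5,000 runs) gives a chance of 0.05, 0.11, 0.22 and 0.35 that the Kaplan–Meier median is at least 6 months, for p = 0, 10%, 20% and 30%.

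The model lets every affected event be erased with no scan catching it, so it is unfavourable in that respect. No OS figure was computed.

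**The case against.** The strongest reply is that the removal sentence is loose wording for leaving study treatment. Section 5.3.2 itself assumes a post-treatment follow-up phase with no prohibitions. Section 5.3 contemplates continued study intervention by agreement of the investigator, the Sponsor and the participant. Section 6.1.6.1 encourages even those who withdraw to complete final-visit activities. This is a plausible account of intent, but the sentence says study, not treatment, and a site could act on it.

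A reader might infer that the participants most likely to be progressing leave both PFS and OS follow-up and that their later deaths go unrecorded. The documents do not support that. Sections 6.1.1.6.3 and 6.1.7.3.3 keep survival follow-up, so OS is lost only if Section 5.3.2 is applied over them. Imaging stops at new anticancer treatment whatever Section 5.3.2 says. A link to worsening disease is documented for radiation only; a removal for a live vaccine loses data but is probably not informative.

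It is also fair to say that the illustration is not evidence about this sentence. Nothing in the documents supports 10% to 30%. At the plan's 3.5-month benchmark, none of these values carries the large-sample median to 6 months; the 5.5-month case crosses because it starts just below the threshold. Section 7 also describes an exploratory pilot without formal comparisons. These points limit the size of the concern. They do not remove the contradiction.

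**Conclusion.** The contradiction is real and rests on the text alone. Section 5.3.2 conflicts with Sections 5.4, 5.5, 6.1.1.6.3 and 6.1.7.3.3, and with its own next paragraph. The harm is conditional: PFS and OS follow-up is lost if a site applies the removal sentence literally. That loss could be informative, with the best support for radiation. The added PFS loss is confined mainly to glucocorticoids, live vaccines, and radiation not treated as new anticancer treatment, and to progression not already documented.

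The size is unknown. The 3.9 to 5.0 months quoted for a true 3.5 months depends on exponential PFS and an assumed share of events censored at the event time, and should be read as an illustration. The case for acting is that lost scans and survival data may not be recoverable, while the correction is small.

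**What to change.** Replace the removal sentence in Section 5.3.2 so that need for or use of a prohibited treatment does not by itself end study participation. State that progression follow-up continues under Section 6.1.4.3 up to that section's own stopping points, and that survival follow-up continues under Section 6.1.7.3.3.

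Separately, reconcile Sections 5.3, 5.3.2 and 5.4 on what happens to study treatment in these participants. The mandatory discontinuation list in Section 5.4 does not name prohibited therapy. This review does not choose that rule.

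Report the number of participants who received each prohibited class, with dates, so that any effect on PFS can be seen.

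The cost is one replaced sentence and the reconciliation, in an amendment. The scans and contacts are already scheduled for participants who stop treatment. The PFS and OS estimates may become slightly less favourable.

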5.3.3 Rescue Medications & Supportive Care

Participants should receive appropriate supportive care measures as deemed necessary by the treating investigator. Suggested supportive care measures for the management of AEs with potential immunologic etiology are outlined along with the dose modification guidelines in Section 5.2.2, [Table 4]. Where appropriate, these guidelines include the use of oral or IV treatment with corticosteroids, as well as additional anti-inflammatory agents if symptoms do not improve with administration of corticosteroids. Note that several courses of steroid tapering may be necessary as symptoms may worsen when the steroid dose is decreased. For each disorder, attempts should be made to rule out other causes such as metastatic disease or bacterial or viral infection, which might require additional supportive care. The treatment guidelines are intended to be applied when the Investigator determines the events to be related to pembrolizumab.

It may be necessary to perform conditional procedures such as bronchoscopy, endoscopy, or skin photography as part of evaluation of the event.

5.4 Participant Discontinuation Criteria

Discontinuation of study intervention does not represent withdrawal from the study.

As certain data on clinical events beyond study intervention discontinuation may be important to the study, they must be collected through the participant's last scheduled follow-up, even if the participant has discontinued study intervention. Therefore, all participants who discontinue study intervention prior to completion of the protocol-specified treatment period will still continue to be monitored in this study and participate in the study visits and procedures as specified in Section 2.3 unless the participant has withdrawn from the study (Section 5.5).

Participants may discontinue study intervention at any time for any reason or be discontinued from the study intervention at the discretion of the investigator should any untoward effect occur. In addition, a participant may be discontinued from study intervention by the investigator or the Sponsor if study intervention is inappropriate, the study plan is violated, or for administrative and/or other safety reasons.

A participant must be discontinued from study treatment but continue to be monitored in the study for any of the following reasons:

- The participant or participant's legally acceptable representative requests to discontinue study intervention
- After prolonged study intervention interruption that prohibits restarting study intervention if agreed upon with the Sponsor
- Radiographic disease progression outlined in Section 6.1.4.
- Any progression or recurrence of any malignancy, or any occurrence of another malignancy that requires active treatment
- Any study intervention-related toxicity specified as a reason for permanent discontinuation as defined in the guidelines for dose modification due to AEs in Section 5.2.2.
- The participant has a medical condition or personal circumstance which, in the opinion of the investigator and/or sponsor, placed the participant at unnecessary risk from continued administration of study treatment.
- The participant has a confirmed positive serum pregnancy test

Completion of pembrolizumab Q3W monotherapy consists of 35 treatments (approximately 2 years). Discontinuation of treatment may be considered for participants who have attained a confirmed complete response (CR) and have been treated for at least 8 cycles (at least 24 weeks), receiving [for monotherapy: at least 2 doses of pembrolizumab; for combination treatment: 2 cycles of the combination including 2 doses of pembrolizumab and at least 80% of the planned doses of lenvatinib beyond the date when the initial CR was declared.

5.5 Participant withdrawal From Study

A participant must be withdrawn from the study if the participant or the participant's legally acceptable representative withdraws consent from the study.

If a participant withdraws from the study, they will no longer receive study intervention or be followed at scheduled protocol visits.

Specified details regarding procedures to be performed at the time of withdrawal from the study are outlined in Section 6.1.6.1.

